12.6.4.1 Sensitivity Analyses: Completers

In order to further evaluate the impact of early discontinuation on GC exposure, the cumulative GC dose in HCe analysis at 24 weeks will be repeated using only subjects who completed the full 24 weeks of treatment.

12.6.5 Additional Analyses

12.6.5.1 Additional BMD parameters

For the change from baseline in bone mineral density, Exploratory Efficacy Endpoint 3.16, the following supportive analyses will be performed by repeating the analysis with the following alternative dependent variables:

1. Spine t-score
2. Spine z-score
3. Hip t-score
4. Hip z-score

Further, bone biomarkers, bone-specific alkaline phosphatase (BSAP), P1NP, C-terminal telopeptide of type I collagen (CTX-1), U-NTx, and Osteocalcin, will be summarized using standard lab summaries with p-values for change from baseline (paired t-test) and difference from placebo (Wilcoxon rank sum).

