1.3.4 Schedule of Treatment Period and Follow-up Activities

	Treatment Period												Follow-up ¹	ET	
	Placebo-Controlled Treatment Period						Open-Label Period								
STUDY VISIT NUMBER	5 Base line	6	7	8	9	10		11	12		13	14	15	16	
STUDY WEEK	0	3	6	12	18	24	27	32	40	46	52	64	76 ²	80	
STUDY DAY ³	1	22	43	85	127	169	190	225	281	323	365	449	533	Last dose +30 days	
Study Visit (V) / Telephone Contact (T) ⁴	V	V ⁵	V	V	V	V	T	V	V	T	V	V	V	V	
Urine pregnancy test for FCP	X		X	X	X	X		X	X		X	X	X	X	
Hormones from blood ^{6,7}	X		X	X	X	X		X	X		X	X	X	X	
Clinical laboratory ^{6,8}	X	X	X	X	X	X		X	X		X	X	X	X	
Urinalysis ⁶	X					X					X		X	X	
HbA1c, fasting glucose and insulin, HOMA-IR ⁶	X					X					X		X	X	
BSAP, P1NP, CTX-1, U-NTx, Osteocalcin	X					X					X		X	X	
PK ^{6,9}		X	X	X		X					X		X	X	
Genetic sample ¹⁰	X														
Vital signs ¹¹ , body weight	X	X	X	X	X	X		X	X		X	X	X	X	
Waist circumference	X					X					X		X	X	
12-lead ECG	X			X		X					X		X	X	
HADS	X			X		X					X		X	X	
SF-36	X					X							X	X	
PGIC						X							X	X	
Study treatment accountability and return of used treatment to site	X	X	X	X	X	X		X	X		X	X	X		
Scrotal ultrasound for males	X ¹²					X ¹³						X ¹³		X ¹³	

	Treatment Period													Follow-up ¹	ET
	Placebo-Controlled Treatment Period						Open-Label Period								
STUDY VISIT NUMBER	5 Base line	6	7	8	9	10		11	12		13	14	15	16	
STUDY WEEK	0	3	6	12	18	24	27	32	40	46	52	64	76 ²	80	
STUDY DAY ³	1	22	43	85	127	169	190	225	281	323	365	449	533	Last dose +30 days	
Study Visit (V) / Telephone Contact (T) ⁴	V	V ⁵	V	V	V	V	T	V	V	T	V	V	V	V	V
DXA scan for body composition and bone mineral density ¹⁴	X					X					X		X		X
Inclusion/exclusion criteria	X														
Concomitant medications	X	X	X	X	X	X	X	X	X	X	X	X	X	X	X
C-SSRS	X			X		X					X		X		X
CGI-I						X							X		X
Randomization to study drug	X														
Dispense study drug ¹⁵	X		X	X	X	X		X	X		X	X			
Study drug accountability		X	X	X	X	X		X	X		X	X	X		X
Monitor background GC dosing	X	X	X	X	X	X	X	X	X	X	X	X	X	X	X
GC dose adjustment telephone contacts ¹⁶	X		X	X	X	X		X	X		X	X			
Dispense HC for stress dosing and perform accountability ¹⁷	X	X	X	X	X	X		X	X		X	X	X	X	X
Review study diary/drug adherence ¹⁸	X	X	X	X	X	X	X	X	X	X	X	X	X	X	X
Review adverse events	X	X	X	X	X	X	X	X	X	X	X	X	X	X	X
Physical examination ¹⁹	X		X	X	X	X		X	X		X	X	X	X	X

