9 STATISTICAL AND ANALYSIS ISSUES

9.1 Adjustments for Covariates

The categorical, randomization stratification variables sex (0 = male, 1 = female) and baseline HCe group (<40 mg/day and \geq 40 mg/day) will be used in all efficacy analyses. Additional categorical covariates may include baseline daily GC type (0 = short-acting, 1 = intermediate acting or combination) and CAH Type (0 =simple virilizing, 1=salt-wasting). Baseline daily GC dose in HCe or BSA adjusted dose may also be included as a continuous covariate. The baseline value of continuous efficacy endpoints will be included as a continuous covariate in statistical models, such mixed model repeated measures (MMRM), analysis of covariance (ANCOVA), or logistic regression.

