9.2 Assessing Normality

Modest departures in the distribution of subject level data from Normality are of no consequence when sample size is high, for example, above a total $N \geq 10$, as Normality of the test statistics, e.g the difference in treatment group means, is assured by the Central Limit Theorem. When based on a total $N \geq 10$, the moment generating function for any test statistic derived from any underlying (non-Normal) probability distribution falls within less than 5% of the ideal moment generating function for the Standard Normal distribution, thus guaranteeing valid inference based upon the Normal approximation. This figure rises to within less than 2.5% of the ideal moment generating function with a total $N \geq 20$.

If, however, departures from Normality are encountered, especially when the effective sample size may be low, a supportive analysis may be performed based on rank values in place of original values.

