12.6.5.5 Key Laboratory and Vital data used in Clinical Outcome Components

Key laboratory and vitals parameters that are used to build key clinical outcomes will be summarized by treatment and post-baseline scheduled time point, based on randomized treatment received at each scheduled time point and will include p-values reporting change from baseline using paired-tests and difference from placebo using Wilcoxon rank sum tests.

- Fasting glucose, HbA1c, and fasting insulin
- Total cholesterol, LDL, HDL, triglycerides
- Blood pressure (systolic and diastolic)

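### Bone-marker, glucose, lipid and blood-pressure comparisons with placebo use a Wilcoxon test with no baseline or stratum adjustment and no stated ranked variable; baseline-adjusted ANCOVA would fit SAP 9.1 and cost only wording

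*SAP*

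**What the plan says.** SAP 12.6.5.1 reports BSAP, P1NP, CTX-1, U-NTx and osteocalcin as laboratory summaries with "p-values for change from baseline (paired t-test) and difference from placebo (Wilcoxon rank sum"). SAP 12.6.5.5 covers fasting glucose, HbA1c, fasting insulin, the four lipids and systolic and diastolic pressure at each scheduled post-baseline time point, with "p-values reporting change from baseline using paired-tests and difference from placebo using Wilcoxon rank sum tests". No covariate or stratum is named in either place, and neither section says whether the Wilcoxon test ranks the change or the value at the visit.

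SAP 9.1 sets the general rule. The two stratification variables, sex and baseline dose below or at least 40 mg/day HCe, "will be used in all efficacy analyses", and "The baseline value of continuous efficacy endpoints will be included as a continuous covariate in statistical models". SAP 9.2 adds that, if Normality is in doubt, "a supportive analysis may be performed based on rank values in place of original values".

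The baselines exist. The schedule in Protocol 1.3.4 has "BSAP, P1NP, CTX-1, U-NTx, Osteocalcin" and "HbA1c, fasting glucose and insulin, HOMA-IR" on Day 1 and at Week 24. Lipids (within the clinical laboratory panel) and blood pressure (within vital signs) are taken on Day 1 and at every clinic visit up to Week 24.

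**The concern.** Where a marker's own baseline is in hand, an unadjusted two-sample test leaves between-subject variation in the comparison that an adjusted test removes. Ranking the change corrects for baseline only partly. Ranking the visit value does not correct for it at all. The plan does not say which is intended, and the two can give very different power on the same data.

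The choice also sits awkwardly beside the rest of the SAP. HOMA-IR, which is computed from glucose and insulin, is modelled with its baseline under 12.6.1, while glucose and insulin themselves get an unadjusted test. The adrenal biomarker responders in 12.6.5.3, a neighbouring subsection, are adjusted for both strata and for the biomarker's baseline.

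At stake is the precision of supportive evidence on bone and metabolic effects of a lower glucocorticoid dose. These two sections promise only p-values for the comparison with placebo. A model would also give an effect estimate with a confidence interval.

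**Working it through.** **1. Does SAP 9.1 reach these tests?** Sections 12.6.5.1 and 12.6.5.5 belong to SAP section 12, Efficacy Analyses. Protocol 8.1.3 and 8.1.4 list the metabolic and bone marker assessments as efficacy assessments, and SAP 4.3.1.3 does so for the metabolic ones. The strata sentence in 9.1 therefore applies on its face. The baseline sentence is narrower: it speaks of continuous efficacy endpoints in statistical models, and a Wilcoxon test is arguably not a model.

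**2. The plan's own power figure.** SAP section 6 gives at least 90% power with 45 per group for 7.25 mg/day in glucocorticoid dose, SD 10.5. Check: 7.25 / (10.5 × √(2/45)) = 3.275; 3.275 − 1.960 = 1.315; Φ(1.315) = 90.6% (90.0% with the t distribution). It reproduces, but it concerns glucocorticoid dose. The documents give no SD, effect size or baseline-to-follow-up correlation (ρ) for any marker, so everything below rests on assumed values.

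**3. Analytic check.** On a Normal scale, the variance of the ANCOVA treatment effect relative to the unadjusted one is (1+ρ)/2 if change is compared and 1−ρ² if the follow-up value is compared. Take an unadjusted test with 80% power, so that 1.960 + 0.842 = 2.802, and compute Φ(2.802/√ratio − 1.960):

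| ρ | ratio, change | power after adjustment | ratio, follow-up value | power after adjustment |
|---|---|---|---|---|
| 0.5 | 0.75 | 89.9% (+9.9) | 0.75 | 89.9% (+9.9) |
| 0.7 | 0.85 | 86.0% (+6.0) | 0.51 | 97.5% (+17.5) |
| 0.8 | 0.90 | 84.0% (+4.0) | 0.36 | 99.7% (+19.7) |

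As ρ rises, the gain over change shrinks and the gain over the follow-up value grows. The ranked variable therefore matters as much as the adjustment.

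**4. Simulation with a skewed marker.** 45 per arm, log-normal, log SD 0.5, two-sided 5%, effect d in log-SD units; 3,000 trials per row, 1,500 for the last. Change is on the raw scale. Power in %:

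| ρ (d) | Wilcoxon, change | Wilcoxon, Week 24 value | rank ANCOVA | log ANCOVA |
|---|---|---|---|---|
| 0.5 (0.62) | 72.7 | 80.9 | 89.6 | 91.5 |
| 0.7 (0.48) | 73.2 | 59.6 | 84.9 | 88.6 |
| 0.8 (0.39) | 72.7 | 43.8 | 80.6 | 86.3 |
| 0.9 (0.28) | 77 | 24 | 79 | 86 |

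**5. Simulation with little skew.** Log SD 0.1, same ρ and d, 2,500 trials. Wilcoxon on change against rank ANCOVA: 79 v 89% at ρ 0.5, 81 v 85% at 0.7, 79 v 81% at 0.8 and 80 v 78% at 0.9. Rank ANCOVA can thus lose slightly at very high correlation.

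**6. Ranges over ρ 0.5 to 0.9 and log SD 0.1 to 0.5, in power points.**

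| | over Wilcoxon on change | over Wilcoxon on Week 24 value |
|---|---|---|
| log ANCOVA | about +4 to +21 | about +10 to +60 |
| rank ANCOVA | about −3 to +18 | about +8 to +54 |

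Type I error stayed near 5% for both ANCOVAs. The strata were not simulated.

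**The case against.** The strongest reply is that nothing here is invalid. A Wilcoxon test in a 1:1 randomised comparison keeps its error rate. These p-values sit under Additional Analyses, outside the hierarchical and Hochberg testing of SAP 9.6. The outcomes that carry more weight are already adjusted: HOMA-IR, BMI, waist and body composition by MMRM or ANCOVA, and secondary endpoint 2.3 (to which cholesterol, LDL and blood pressure contribute through Table 8) by logistic regression with the strata and the baseline number of risk factors. All of this stands, and it limits the point to a refinement.

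Part of the gain over Wilcoxon on change also comes from scale. With log SD 0.5, ranking the log change instead of the raw change gives about 80 to 81% power at ρ 0.5 to 0.8, which leaves rank ANCOVA under 2 points ahead at ρ 0.8. That stands too. It is one reason to prefer log-scale ANCOVA, which had the higher power in every setting run.

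A reader might infer that a definite amount of power, say 8 to 17 points, is being lost. The documents do not support any fixed figure, because correlation, skewness and ranked variable are all unstated. A reader might also infer that the trial's case for clinical benefit rests on these tests. The SAP presents them as supportive summaries, and no study conclusion is made to depend on them.

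**Conclusion.** The two sections plan a between-arm test that ignores available baselines, does not follow the SAP 9.1 rule on strata, and leaves its ranked variable undefined. Baseline-adjusted ANCOVA would be at least as defensible and, on the log scale, more powerful in every setting examined. The size is conditional on the assumptions stated with the simulations: 45 per arm with complete data, log-normal markers, and correlation and skewness chosen by assumption. If change is ranked and correlation is high, the gain is small and for rank ANCOVA can be slightly negative. If the visit value is ranked and correlation is high, the gain is large. Because the p-values are supportive and exploratory, no confirmatory conclusion changes. This is a worthwhile improvement, not a flaw that threatens the trial.

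**What to change.** In SAP 12.6.5.1 and 12.6.5.5, for each post-baseline visit that has a placebo comparison:

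- Make ANCOVA on the log scale the main between-arm test, with log baseline, treatment, sex and the <40/≥40 mg/day HCe stratum. Report the treatment estimate and its 95% CI, back-transformed to a ratio.
- Use rank ANCOVA with the same terms where the log model fits poorly. SAP 9.2 already provides for analysis on ranks.
- Keep the Wilcoxon p-value as supportive if wanted, and state whether change or the visit value is ranked.

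Protocol 9.4.7.5 names t-tests for vital-sign p-values, while SAP 12.6.5.5 names Wilcoxon for blood pressure. SAP section 3 says the SAP governs, but the difference should be recorded in SAP section 14 along with this change.

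The cost is SAP wording and minor programming before unblinding. No new data, visits or subjects are needed.

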12.6.5.2 DXA Body Composition Parameters

Under Exploratory Efficacy Endpoints 3.14 and 3.15, changes in body composition as measured by DXA from baseline to Week 24 and Week 52 will be compared between tildacerfont and placebo; these parameters are percent total fat, and total percent lean mass .

12.6.5.3 Additional Adrenal Biomarker Analyses

The following Week 24 and Week 52 analyses will provide additional context to aid in the interpretation of adrenal biomarker data.

Table 16 Adrenal Biomarker Responder Definitions

Endpoint	Definition
Proportion of subjects with $A4 \leq ULN$	1 $A4 \leq ULN$ 0 $A4 > ULN$ or missing
Proportion of subjects with $A4 \leq 1.5 \times ULN$	1 $A4 \leq 1.5 \times ULN$ 0 $A4 > 1.5 \times ULN$ or missing
Proportion of subjects with $A4 \leq 2 \times ULN$	1 $A4 \leq 2 \times ULN$ 0 $A4 > 2 \times ULN$ or missing
Proportion of subjects with $17OHP \leq Target$	1 $17OHP \leq Target$ 0 $17OHP > Target$ or missing

In keeping with the analysis of Secondary Efficacy Endpoint 2.1, a logistic regression model will be used to evaluate the endpoints described in [Table 17](#). The model will include the responder indicator as the dependent variable; treatment group (0: placebo, 1: tildacerfont); the randomization strata: sex (0: male, 1: female) and baseline GC dose (in HCe, 0: < 40 mg/day, 1: ≥ 40 mg/day); and baseline GC type (0: short-acting, 1: intermediate-acting or combination) as categorical explanatory variables. The baseline value for the adrenal biomarker will be included as a variable.

12.6.5.4 Additional PGIC and CGI-I Analyses

Both patients' (PGIC) and clinician's (CGI-I) global impression of improvement scales will be summarized at Weeks 24 and 76. Summaries will include the count and proportion of subjects at each point on the Likert scale as well as an 8-point descriptive summary. At Week 24, a t-test will be used to derive a p-value on the mean score of the placebo and tildacerfont groups.

12.6.5.5 Key Laboratory and Vital data used in Clinical Outcome Components

Key laboratory and vitals parameters that are used to build key clinical outcomes will be summarized by treatment and post-baseline scheduled time point, based on randomized treatment received at each scheduled time point and will include p-values reporting change from baseline using paired-tests and difference from placebo using Wilcoxon rank sum tests.

- Fasting glucose, HbA1c, and fasting insulin
- Total cholesterol, LDL, HDL, triglycerides
- Blood pressure (systolic and diastolic)

12.6.5.6 Compliance to A4 algorithm

Principal investigators may deviate due to medical or patient reasons from the protocol specified A4 GC change algorithm. A summary will be provided to compare adherence to the GC dosing algorithm by summarizing the proportion of assessment outcomes that followed the protocol algorithm by nominal time point, by treatment group and overall.

12.7 Figures

Efficacy data will be plotted for primary and key secondary endpoints. The following plots are planned:

- LS Means and 95% CI of Change from Baseline in GC dose by Visit
- Proportion of subjects with GC dose ≤ 11 mg/m²/day in HCe and A4 ≤ 1.2 times baseline or A4 \leq ULN through Week 24
- Proportion of subjects with baseline GC dose ≤ 35 mg HCe who achieve GC dose ≤ 11 mg/m²/day in HCe and A4 ≤ 1.2 times baseline or \leq ULN at Week 24
- Proportion of subjects with improvement in at least one cardiovascular risk factor at Week 24

Additional figures may be produced for other endpoints as deemed appropriate. The following plots are planned, and additional types (forest plots; cumulative distribution plots) may be provided to facilitate illustration of the study results.

13 SAFETY ANALYSES

Safety will be evaluated by AEs, SAEs, AESIs, clinical laboratory, vital, ECG findings, monitoring for suicide risk and depression/anxiety, as well as physical examination. All analyses of safety data will be performed using the safety analysis set, based on the actual treatment a subject received. All descriptive statistics will be presented by treatment group and treatment period.

13.1 Adverse Events

All reported AEs (including non-TEAEs) will be listed. Separate listings will be provided for SAEs, AESIs, and TEAEs leading to study drug discontinuation. If a subject reported the same TEAE on multiple occasions, the highest severity (severe > moderate > mild) or study drug relationship (related > probable > possible > unlikely > unrelated) recorded for the event will be summarized. All TEAE summary tables will present the number and percentages of subjects reporting TEAEs, unless otherwise specified.

13.1.1 Overall Summary of TEAEs

Overall summary of TEAEs will be presented by study period (i.e., Placebo-Controlled Treatment, and Open-Label Treatment) and treatment group. Subjects will be counted only once at the highest severity when summarizing TEAE by severity (severe > moderate > mild).

13.1.2 Summary of TEAEs by System Organ Class and Preferred Term

In addition, TEAEs will be summarized by MedDRA SOC and PT. Each summary table will be presented by study period (i.e., Placebo-Controlled Treatment, and Open-Label Treatment) and treatment group as well as overall by treatment group. A subject experiencing multiple occurrences of an adverse event will be counted only once for each PT. Subjects with multiple PTs within a SOC will be counted only once for that SOC. The summaries will be presented for

the following; if a summary does not include more than 20 events, summaries by PT only (Section 13.1.3) may be deemed to be sufficient:

- TEAEs by SOC and PT
- Severe TEAEs by SOC and PT
- Study drug-related TEAEs by SOC and PT
- Severe Study drug-related TEAEs by SOC and PT
- AESIs by SOC and PT
- AESI of liver Events
- Serious TEAEs by SOC and PT
- Serious Study drug-related TEAEs by SOC and PT
- TEAEs leading to study drug discontinuation by SOC and PT
- TEAEs leading to death by SOC and PT

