7.4 Safety Analysis Set

The Safety (SAF) Analysis Set is defined as all subjects who received at least one dose of study drug (placebo or tildacerfont). The safety analysis set, which will be based on the actual treatment received, will be used for evaluation of general medical history, study drug exposure, concomitant medication, and safety. Placebo-treated subjects who received any amount of tildacerfont during the Open-Label Period will be assigned to the tildacerfont treatment group from the time when tildacerfont was received.

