8.1 Presentation of Summary Statistics

For most summary statistics, data will be displayed in tabular format. Unless otherwise specified, continuous adrenal biomarkers (A4, 17-OHP, ACTH) will be summarized using a 11-point descriptive statistics (i.e., n, mean, standard deviation [SD], median, 25% quartile [Q1], 75% quartile [Q3], minimum, maximum, geometric mean, geometric coefficient of variance [CV%],

95% confidence interval [CI] for geometric mean [including geometric mean ratio and its 95% CI]. All other continuous variables will be summarized using an 8-point descriptive summary (n, mean, SD, median, Q1, Q3, minimum, and maximum). The same number of decimal places as in the observed value will be presented when reporting minimum and maximum; 1 additional decimal place than in the observed value will be presented when reporting mean, median, Q1, Q3, geometric mean, 95% CI; 2 additional decimal places than in the observed value will be presented when reporting SD. Geometric CV% will be reported to one decimal place.

All categorical/qualitative data will be presented using the frequency of events and percentages. All percentages will be presented to 1 decimal place, unless otherwise specified. Percentages equal to 100 will be presented as 100% and percentages will not be presented for zero frequencies. Where individual variable values are missing, categorical data will be summarized based on reduced denominators (i.e., only subjects with available data will be included in the denominators).

For summaries of AEs and concomitant medications (CMs), the percentages will be based on the number of subjects who received study drug.

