13.1.3 Summary of TEAEs by Preferred Term

In addition, TEAEs will be summarized by MedDRA PT. Each summary table will be presented by study period (i.e., Placebo-Controlled Treatment, and Open-Label Treatment) and treatment group as overall by treatment group. A subject experiencing multiple occurrences of an adverse event will be counted only once for each PT. The summaries will be presented for:

- TEAEs by PT
- Severe TEAEs by PT
- Study drug-related TEAEs by PT
- Severe Study drug-related TEAEs by PT
- AESIs by PT
- Serious TEAEs by PT
- Serious Study drug-related TEAEs by PT
- TEAEs leading to study drug discontinuation by PT
- TEAEs leading to death by PT

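### At the final analysis, the overall-by-treatment columns of the SAP 13.1.2 and 13.1.3 TEAE tables set crude percentages from 24 weeks of placebo beside 52 or 76 weeks of tildacerfont

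*SAP*

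**What the plan says.** SAP 13.1.2 (tables by system organ class and preferred term) asks for each table by study period and treatment group, "as well as overall by treatment group". SAP 13.1.3 (tables by preferred term) gives the same layout: "treatment group as overall by treatment group". The Overall Summary of TEAEs in SAP 13.1.1 is by period and treatment group only.

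Four other rules fix what the overall columns will contain:

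- **Metric** (SAP 13.1): "All TEAE summary tables will present the number and percentages of subjects reporting TEAEs, unless otherwise specified".
- **Denominator** (SAP 8.1): "the percentages will be based on the number of subjects who received study drug".
- **Counting** (SAP 13.1.2): "A subject experiencing multiple occurrences of an adverse event will be counted only once for each PT".
- **Treatment assignment**: SAP 13 states "All analyses of safety data will be performed using the safety analysis set, based on the actual treatment a subject received". SAP 7.4 adds that placebo subjects who go on to take open-label drug "will be assigned to the tildacerfont treatment group from the time when tildacerfont was received".

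SAP 11.1 and protocol 9.4.7.1 summarise exposure, but neither document uses it as a denominator for adverse events.

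**The concern.** A once-per-subject percentage depends on how long each subject is watched. When two columns cover very different lengths of treatment, the one with longer follow-up will tend to show more subjects with an event even if the drug adds no risk. The overall columns have this form: one treatment is given for 24 weeks only, and the other for 52 or 76.

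The layout applies to all the listed tables in these two sections, including serious TEAEs, AESIs, liver AESIs, discontinuations and deaths. Counts there may be small, and an apparent doubling is easy to misread. SAP 3 says the planned analyses may be used in regulatory submissions and manuscripts, so the columns may be read away from the exposure tables. Crossed-over subjects also appear in both columns, so the two groups are neither independent nor a randomised contrast.

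**Working it through.** **Inputs.** Placebo-controlled period 24 weeks and open-label period 52 weeks (SAP 4); 1:1 allocation (SAP 4.1); 45 planned per arm (SAP 6). The documents give no adverse event rate, so the 24-week incidence p is an assumption, shown over a range.

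**1. Reproduce the plan's exposure figures.** 24 + 52 = 76 weeks of tildacerfont for those randomised to it, and 52 weeks for those randomised to placebo. Both match the maxima in SAP 4.

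**2. Exposure per column, full follow-up.** The mean per subject on tildacerfont is (76 + 52)/2 = 64 weeks, against 24 on placebo, a ratio of 64/24 = 2.67. Person-years, at 52 weeks to the year, are 45 × 24/52 = 20.8 on placebo and 45 × 76/52 + 45 × 52/52 = 65.8 + 45.0 = 110.8 on tildacerfont. The tildacerfont column also has twice as many subjects (90 v 45), so the per-subject ratio of 2.67 is what drives the percentages.

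**3. Crude percentages at equal risk.** With the same constant hazard on both treatments, P(t) = 1 − (1 − p)^(t/24). The overall tildacerfont entry is the mean of P(52) and P(76). For p = 10%: P(52) = 1 − 0.9^(52/24) = 20.4%, P(76) = 1 − 0.9^(76/24) = 28.4%, mean 24.4%.

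| Placebo, 24 wk (assumed) | P(52) | P(76) | Tildacerfont overall | Ratio |
|---|---|---|---|---|
| 5% | 10.5% | 15.0% | 12.8% | 2.55 |
| 10% | 20.4% | 28.4% | 24.4% | 2.44 |
| 20% | 38.3% | 50.7% | 44.5% | 2.23 |
| 30% | 53.8% | 67.7% | 60.8% | 2.03 |
| 50% | 77.7% | 88.9% | 83.3% | 1.67 |
| 90% | 99.3% | 99.9% | 99.6% | 1.11 |

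**4. Sensitivity, p = 10%.**

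- If half the subjects stop tildacerfont after 24 weeks on it, the entry is 0.5 × 10% + 0.25 × (20.4% + 28.4%) = 17.2%, a ratio of 1.72.
- If the 30-day window after last dose (SAP 8.3.18.1) is added to tildacerfont only, it is 25.8%, a ratio of 2.58.

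**5. What an exposure-adjusted figure would show.** First events per 100 person-years at risk are −ln(1 − p) × (52/24) × 100. At p = 10% this is 0.1054 × 2.167 × 100 = 22.8 in both columns, a ratio of 1.00. The 24 v 24 week comparison gives 10% v 10%.

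**The case against.** The strongest case is that the plan already contains the fair comparison. The same tables carry placebo-controlled columns by treatment group, 24 v 24 weeks. SAP Table 5 assigns the safety endpoint (5.1, AEs and SAEs) to the Primary Analysis, which uses data locked through Week 24, where overall and placebo-controlled columns essentially coincide. The TEAE summaries are descriptive, with no test or risk difference on the overall columns. Exposure duration is tabulated, so an attentive reader can see the imbalance. All of this stands, and it limits the point to how the Week 76 tables may be read.

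Two further replies carry less weight. The overall columns might mean randomised arm. SAP 7.4 and SAP 13 point to actual treatment, and under the other reading the placebo column would mix placebo and drug time, so it would still not be a clean comparator. The table shells may also carry footnotes. SAP 8 refers to mock shells in an appendix that is not in the text available here, so headers and footnotes could not be checked.

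A reader might infer that every TEAE table is affected, or that the trial's safety comparison is biased. The documents support neither: SAP 13.1.1 is by period only, and the placebo-controlled columns are sound. A reader might also take the person-years (20.8 v 110.8, over fivefold) as the size of the distortion. Much of that gap is the doubled number of subjects on tildacerfont, not longer follow-up of each.

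**Conclusion.** The point holds for the overall columns of the SAP 13.1.2 and 13.1.3 tables at the final analysis. As specified, those columns are not comparable, and at equal risk they would tend to show an excess on tildacerfont. It is a minor point of presentation.

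The size is conditional. About 2.0- to 2.6-fold for 24-week incidences of 5% to 30% assumes a constant, equal hazard, full crossover and full follow-up, with incidences that are not in the documents. Dropout shrinks it, very common events shrink the ratio, and early-clustering events shrink it too.

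The direction needs less. For subjects randomised to tildacerfont, a once-per-term count cannot fall between Week 24 and Week 76. For crossed-over subjects it depends on events continuing after Week 24. If events were confined to the first weeks after randomisation, their half of the column would add few and the excess could disappear. It would therefore be too strong to say that the tables will show a large excess. The supported statement is that the overall columns cannot be read as a treatment comparison.

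**What to change.** In SAP 13.1.2 and 13.1.3, for the final analysis, do one of the following:

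- replace the overall placebo and tildacerfont columns with a single any-tildacerfont column without a placebo comparator; or
- keep both and add, beside the crude percentages, subjects with an event per 100 person-years at risk, with the person-years shown.

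In either case, add a sentence to SAP 13.1 that treatment comparisons of adverse events rest on the placebo-controlled period, and keep the crude percentages for that period as planned.

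The cost is minor programming: SAP 8.3.19.4 already derives exposure duration from first and last dose dates in each treatment period. Conduct, sample size and efficacy analyses are untouched. The drawback of person-year rates is that they assume a roughly constant hazard. Long open-label time can dilute events that occur early on drug, which could hide a signal. That is why the crude placebo-controlled percentages should stay, and it favours the single any-tildacerfont column if only one change is made.
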